14.1.3 Full Analysis Set

The Full Analysis Set (FAS) will consist of all study participants in the SS who have a Baseline and least 1 post-Baseline iRODS measurement.

The FAS is the primary analysis set for efficacy analyses.

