3.3 Definition of Baseline values

For all study variables, the Baseline values for study participants treated with rozanolixizumab in the parent study (ie, CIDP01) will be the Baseline values from the parent study. For study participants treated with placebo in the parent study, the Baseline values will be the ones present at Baseline in CIDP04 (Visit 2 or if missing, the Screening Visit value (if applicable)). Note this Visit 2 value may be corresponding to the last value registered into CIDP01 as these may be the same visit.

Scheduled or unscheduled measurements can be used as the Baseline value. Expected measurement-specific Baseline timepoints are presented in [Table 3-1](#). If an unscheduled measurement occurs after the planned baseline measurement timepoint but before dosing, then the unscheduled measurement will be used as the baseline value.

Table 3–1: Expected Baseline

Measurement	Definition of Baseline
Safety data: 
• Safety Lab (Clinical chemistry, Hematology, Urinalysis)• ECG• Vital signs• Total protein, albumin, α- and β-globulins	For study participants treated with rozanolixizumab in parent study CIDP01: Safety labs, vital signs, total protein, albumin, α - and β -globulin: Baseline visit (Day 1) of parent study, if missing Screening visit of parent study (pre-dose value, if applicable). For study participants treated with placebo in the parent study: Safety labs, vital signs, total protein, albumin, α - and β -globulin: Baseline visit (Day 1) in CIDP04, if missing Screening visit (if applicable) (pre-dose value, if applicable). ECG: mean of triplicate values of Baseline visit (Day 1) in CIDP04. If missing Baseline visit, mean of triplicate values of Screening visit (if applicable).
Efficacy data 
• iRODS• INCAT• Grip strength (assessed by site personnel)• RT-MRC and original MRC• Fatigue score• CIDP PRO• PGIS• PGIC	For study participants treated with rozanolixizumab in parent study CIDP01: Baseline visit (Day 1) in CIDP01, if missing Screening visit For study participants treated with placebo in the parent study: Baseline visit (Day 1) in CIDP04, if missing Screening visit (where applicable)

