3.5.2 Safety Set

The Safety Set (SS) will consist of all enrolled study participants who were administered at least one dose of rozanolixizumab in CIDP04.

All safety variables will be analyzed using the SS.

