3.5.3 Full Analysis Set

The Full Analysis Set (FAS) will consist of all participants in the SS, who have a Baseline and at least one valid post-Baseline iRODS measurement up to Visit 26/PEOT (inclusively).

Measurements are considered invalid if the participant received rescue medication before the assessment of iRODS. Assessments collected at the same day as first intake of rescue medication are considered valid. Invalid measurements will not be used for summary tables, but kept in listings.

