4.2 Handling of dropouts or missing data

4.2.1 Efficacy data

For study participants who prematurely withdraw for any reason before Visit 26, data collected during the PEOT Visit will be mapped to the closest missing visit according to the visit schedule utilizing the relative day in study to a maximum of Visit 26 (end of treatment period). However, if a participant receives rescue medication prior to the PEOT visit, any efficacy assessment post intake will be regarded invalid and only listed. Assessments on the same day as first intake of rescue medication are acceptable for analysis.

Study participants administered an Ig infusion rescue medication during the treatment phase will be considered relapsed even in case no relapse was documented. Missing relapse data, i.e. data for any relapse event definition, will be considered missing. In case of drop-out, if no relapse occurs or rescue medication is taken until PEOT visit (inclusively), the subject will be censored for time-to-event analysis at the date of PEOT visit.

Participants are asked to record three grip strength score assessments at each day. The efficacy parameter will be derived from grip strength scores taken by a participant up to five days prior to the first IMP (for Baseline value) or visit date (for post Baseline visit value):

1. Maximum of grip strength assessments available at a particular day
2. Mean of maximum grip strength over most recent three non-missing days - up to a maximum of five days
3. Missing values: In case all three assessments of a day are missing, the maximum grip strength score will be set to missing and will not be used for the derived score. In this case the preceding day's maximum grip strength score will be used instead, but no later than the fifth day prior to the first IMP or visit date respectively. In case data is entirely missing during the last five days prior to the visit, the derived score will be set to missing.

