8 EFFICACY ANALYSES

All summaries of efficacy data will be performed on the FAS. Additional outputs are repeated for the MFAS where indicated. Listings will be based on the SS. Treatment group assignment for efficacy data presentation will be according to the actual treatment regimen.

8.1 iRODS

8.1.1 iRODS scores

The iRODS is a linearly weighted patient-reported outcome measure (questionnaire) that specifically captures activity and social participation limitations in patients with CIDP. The iRODS scale was constructed based on the World Health Organization (WHO) International Classification of Functioning, Disability and Health, literature search, and patient interviews.

All 24 items of iRODS meet Rasch model expectations. The questionnaire consists of 24 items (including eating, taking a shower, walking a flight of stairs, standing for hours, etc.) and assesses a patient's perception of their ability to perform daily and social activities. Patients have

3 response options: 0=impossible to perform; 1=performed with difficulty; and 2=easily performed, performed without difficulty.

The raw sum scores of iRODS (range 0 to 48) is an ordinal scale and does not allow for easy interpretation of differences. For this reason, the ordinal scale will be translated to log odds units (logits) scale using the nomogram in [Section 13.1](#), placing patients' estimates on the same logit scale. The primary analysis and iRODS summary will be performed on logit locations. For easier interpretation the person locations (logits) will be translated to centile metric scores changing from 0 (most severe activity and social participation restrictions) to 100 (no activity and social participation limitations).

Both transformed and untransformed data will be listed and summarized by treatment group for each scheduled assessment during the Treatment and Observation Period.

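### The SAP's Full Analysis Set leaves a newly treated participant rescued before any post-dose iRODS out of the relapse and rescue summaries, but keeps a previously treated participant with the same course

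*Protocol*

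**What the plan says.** Protocol 14.1.3 admits to the FAS "all study participants in the SS who have a Baseline and least 1 post-Baseline iRODS measurement". It sets no condition on rescue.

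SAP 3.5.3 narrows this to "at least one valid post-Baseline iRODS measurement up to Visit 26/PEOT (inclusively" and defines validity: "Measurements are considered invalid if the participant received rescue medication before the assessment of iRODS". There is one exception: "Assessments collected at the same day as first intake of rescue medication are considered valid". SAP 3.9 declares the change.

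SAP 8 states: "All summaries of efficacy data will be performed on the FAS". Listings use the Safety Set. SAP 8.1.2 repeats the FAS for iRODS relapse, and SAP 8.2.2, 8.3.2, 8.3.3 and 8.4 carry the same methods to INCAT, grip strength and composite relapse. Rescue use (SAP 8.5) also sits inside section 8.

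SAP 4.2.1 makes rescue an event: "Study participants administered an Ig infusion rescue medication during the treatment phase will be considered relapsed even in case no relapse was documented".

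SAP 3.3 sets Baseline by former arm. For one group, "the Baseline values for study participants treated with rozanolixizumab in the parent study (ie, CIDP01) will be the Baseline values from the parent study"; for former placebo participants it is the CIDP04 Baseline. SAP 3.5.2 limits the Safety Set to those "who were administered at least one dose of rozanolixizumab in CIDP04". SAP 3.5.3 gives the FAS score an upper time limit but no starting point in CIDP04.

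**The concern.** Entry to the analysis set depends on the outcome being estimated. Someone who fails very early and is rescued can lose the score needed to be counted, so the rule that rescue is a relapse never reaches that person in the tables or Kaplan-Meier summaries.

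The condition also works differently in the two groups that SAP 3.6 displays side by side. Previously treated participants can meet it with a score from the parent study; newly treated participants cannot. An identical early failure would then count as a relapse in one group and be absent from numerator and denominator in the other.

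Rescue use, INCAT relapse and grip-strength relapse do not need an iRODS score to be determined, so the condition serves no purpose for them.

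**Working it through.** The plan has no figure to reproduce: Protocol 14.8 and SAP 2.4 give no sample size calculation, and N is redacted. The check applies the definitions to two participants, then sizes the effect with assumed counts.

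**1. Same CIDP04 course, two groups.** Both are dosed at Visit 2, receive Ig rescue before Visit 3 with no iRODS between first dose and rescue (nor on the rescue day), and complete an iRODS later at PEOT.

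| Step | Newly treated | Previously treated |
|---|---|---|
| Safety Set (SAP 3.5.2) | in | in |
| Baseline (SAP 3.3) | CIDP04 Visit 2 | CIDP01 Day 1 |
| Post-Baseline iRODS before rescue | none | CIDP01 scores after Day 1 |
| PEOT iRODS (SAP 3.5.3) | invalid | invalid |
| FAS | out | in |
| Relapse and rescue rates | absent | counted as relapsed (SAP 4.2.1) |

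For direct entrants, SAP 3.1 confirms that the last CIDP01 value is used as Visit 2. For previously treated participants with a gap, the right-hand column assumes an earlier CIDP01 on-treatment iRODS; nothing in SAP 3.5.3 rules it out.

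Under Protocol 14.1.3 alone, the PEOT score would keep the newly treated participant in. The exclusion comes from SAP 3.5.3 and the difference between groups from SAP 3.3.

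**2. Time window.** The first scheduled post-dose iRODS is Visit 3 (Week 2), 7 days after Visit 2 with a window of 2 days either side: 7 − 2 = 5 to 7 + 2 = 9 days.

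**3. Size per case.** Let n be the newly treated Safety Set count, x the other relapsed participants, and k those rescued before any valid post-Baseline iRODS.

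- Safety Set rate = (x + k)/n
- FAS rate = x/(n − k)
- For k = 1, the difference is (n − 1 − x)/[n(n − 1)]

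| n | x | Safety Set | FAS | Difference (points) |
|---|---|---|---|---|
| 10 | 1 | 2/10 = 20.0% | 1/9 = 11.1% | 8.9 |
| 10 | 2 | 3/10 = 30.0% | 2/9 = 22.2% | 7.8 |
| 15 | 4 | 5/15 = 33.3% | 4/14 = 28.6% | 4.8 |
| 20 | 4 | 5/20 = 25.0% | 4/19 = 21.1% | 3.9 |
| 30 | 4 | 5/30 = 16.7% | 4/29 = 13.8% | 2.9 |

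Two such participants (k = 2), over n = 10 to 30 and x = 2 or 4, give 5.7 to 15.0 points.

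For scale, the 95% Wald interval in the n = 20 row is 6.0% to 44.0% on the Safety Set and 2.7% to 39.4% on the FAS. One case moves the estimate by much less than its sampling error.

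**4. Opposite direction.** A newly treated participant who leaves without rescue and without a post-dose iRODS is also outside the FAS. Set against a Safety Set rate that counts this person as a non-event, the exclusion raises the rate: 2/10 = 20.0% becomes 2/9 = 22.2%, and 4/20 = 20.0% becomes 4/19 = 21.1%.

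**The case against.** The triggering case is rare by design. Protocol 7.8.3 ties rescue to scored relapse criteria. iRODS comes before other assessments at a visit, and a same-day score counts. All visits in the first 4 weeks are on site, Visits 3 to 6 each include iRODS, and Protocol 8.6 allows unscheduled efficacy visits. Participants entering after a gap are stabilised on immunoglobulin first, and placebo direct entrants completed CIDP01 treatment without relapse. This stands and limits the scope. It does not close the gap: a missed early visit followed by rescue has the same effect, and SAP 8.4 admits a relapse reported by the investigator for another reason, which need not come with a score.

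The exclusion would also be visible. SAP 5.1 tabulates analysis-set counts by group and lists membership, and relapse and rescue are listed on the Safety Set. That stands too, but a visible exclusion still leaves the summary rate short of an event.

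Counting CIDP01 scores as post-Baseline for the previously treated group follows from timing their relapse from CIDP01 Day 1. As a choice of origin that is coherent. The difficulty is that it decides membership differently in the two groups.

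Three stronger readings are tempting but unsupported. A reader might infer that the protocol's own FAS definition removes rescued participants; it does not, since it has no validity condition. A reader might infer that these participants disappear from the report; they stay in the Safety Set listings and safety tables. A reader might infer that a previously treated participant enters the FAS on parent-study data alone; that holds only for the iRODS condition, since one CIDP04 dose is still required.

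**Conclusion.** The point holds as a narrow defect in SAP 3.5.3 read with 3.3 and 8. A newly treated participant rescued before any post-dose iRODS is left out of the relapse and rescue summaries, against the intent of SAP 4.2.1; a previously treated participant with the same course is counted.

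Each such case would understate the newly treated rate by roughly 3 to 9 points in assumed groups of 10 to 30 with 1 to 4 other relapses. Those counts are assumptions, and nothing in the documents indicates that any first-week rescue occurred or is expected. It would therefore be wrong to conclude that the newly treated rate is known to be biased downward by that amount. The net direction is also not fixed, because early dropouts without rescue are excluded by the same rule.

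Efficacy is a secondary objective with descriptive analysis. Priority is minor to moderate: few participants, but an outcome-dependent exclusion that is easy to remove.

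**What to change.** - Summarise relapse (each criterion and the composite), time to relapse, rescue use and time to rescue on the Safety Set, counting Ig rescue as relapse as SAP 4.2.1 already does.
- State how to treat Safety Set participants with no post-dose assessment and no rescue, since SAP 4.2.1 leaves missing relapse data missing. In the Kaplan-Meier analysis, censor them at their last available CIDP04 contact. In the proportions, show them as a separate not-assessed count and not as non-relapsed.
- Keep the FAS for iRODS score summaries, and require a Baseline plus one or more valid iRODS scores dated after the first CIDP04 dose. This changes membership only; the Baseline used for change scores is untouched.
- Record the change in SAP 3.9. There is a precedent there: the pharmacodynamic set was moved from the FAS to the Safety Set so that missing efficacy results would not exclude data.

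The cost is wording in SAP 3.5.3 and 8, with the entry in 3.9, and rerunning the affected tables. No new data are needed. The reported relapse rate may become slightly less favourable.

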14.1.4 Pharmacokinetic Per-Protocol Set

The Pharmacokinetic Per-Protocol Set (PK-PPS) is a subset of the SS, consisting of those study participants who had no important protocol deviation affecting the plasma concentration of rozanolixizumab. Post-Baseline deviations will not necessarily lead to total exclusion of a study participant from the PK-PPS but may lead to exclusion of specific data.

14.1.5 Pharmacodynamic Per-Protocol Set

The Pharmacodynamic Per-Protocol Set (PD-PPS) is a subset of the FAS, consisting of those study participants who had no important protocol deviation affecting the serum concentrations of total IgG or IgG subclasses. Post-Baseline deviations will not necessarily lead to total exclusion of a study participant from the PD-PPS but may lead to exclusion of specific data.

14.2 General statistical considerations

All analyses will be performed using SAS® version 9.2 or later (SAS Institute, Cary, NC, USA). Continuous variables will be summarized by visit (where applicable) with the statistics mean, standard deviation (SD), median, minimum, and maximum. Categorical variables will be summarized by visit (where applicable) with frequency counts and percentages.

Data listings containing all documented data and all calculated data will be generated.

Baseline will be the last nonmissing data collected prior to the first dose of IMP, and measurement-specific Baseline values will be defined in the SAP.

14.3 Planned safety analyses

14.3.1 Safety analyses

The incidence of study participants with TEAEs will be determined. Furthermore, the absolute and relative frequencies for study participants with a given TEAE with respect to the preferred term according to the latest available version of the Medical Dictionary for Regulatory Activities

(MedDRA®), will be determined within each system organ class. Additional tables will summarize TEAEs by maximum severity and causal relationship with rozanolixizumab, as judged by the investigator. Adverse events will be categorized by severity according to the National Institutes for Health CTCAE version 5.0 grading (National Institutes for Health, 2017). In case the CTCAE grading is not available, the intensity (mild/moderate/severe) will be utilized. The TEAEs leading to discontinuation of IMP and the serious TEAEs will also be summarized. The action taken, time of onset relative to dosing, actual dose received, and duration of each AE will be listed only.

For the continuous laboratory variables, the values and changes from Baseline will be descriptively summarized at each time point. For categorized values according to the reference range, shift tables from Baseline to each post-Baseline time point will be presented for selected variables to be defined in the SAP. Values outside the reference range will be flagged in the data listings.

Descriptive statistics will be presented for ECG value and changes from Baseline over time based on the mean of the triplicate assessments at each time point. Categorical analyses for QTc, eg, QTc increase >60msec, will also be performed.

Descriptive statistics will be reported for all vital sign measurements (including BP, PR, temperature, and body weight). Measured values and changes from Baseline will be summarized by time point.

Physical and neurological examination findings and the results of any pregnancy testing will be presented in listings only. Results will be listed for any study participants who complete a headache questionnaire, undergo stool sampling, or lumbar puncture, etc.

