4.1.2 Other safety variables

The other safety variables are:

- TEAEs leading to permanent withdrawal of IMP
- Vital signs values and changes from Baseline (systolic and diastolic BP, PR, body temperature, and body weight) at each scheduled assessment during the Treatment and Observation Periods
- Physical examination findings
- Neurological examination findings
- 12-lead ECG values and change from Baseline at each scheduled assessment during the Treatment and Observation Periods
- Laboratory values and changes from Baseline at each scheduled assessment during the Treatment and Observation Periods (hematology, clinical chemistry, and urinalysis)
- Tuberculosis Signs and Symptoms Questionnaire at each scheduled assessment during the Treatment and Observation Periods

- Values and change from Baseline in concentrations of total protein, albumin, α - and β -globulins at each scheduled assessment during the Treatment and Observation Periods

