2 PROTOCOL SUMMARY

2.1 Study objectives

2.1.1 Primary objective

The primary objective of the study is to assess long-term safety and tolerability of weekly doses of rozanolixizumab in study participants with chronic inflammatory demyelinating polyradiculoneuropathy (CIDP).

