2.2.1.2 Other safety variables

The other safety variables are:

- TEAEs leading to permanent withdrawal of investigational medicinal product (IMP)
- Vital sign values and changes from Baseline (systolic and diastolic blood pressure (BP), pulse rate (PR), body temperature, and body weight) at each scheduled assessment during Treatment and Observation Periods
- Physical examination findings
- Neurological examination findings
- 12-lead electrocardiogram (ECG) values and change from Baseline at each scheduled assessment during Treatment and Observation Periods
- Laboratory values and changes from Baseline at each scheduled assessment during Treatment and Observation Periods (hematology, clinical chemistry and urinalysis)
- Tuberculosis Signs and Symptoms Questionnaire at each scheduled assessment during Treatment and Observation Periods
- Values and change from Baseline in concentrations of total protein, albumin, α - and β -globulins at each scheduled assessment during Treatment and Observation Periods

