3.6 Treatment assignment and treatment groups

All study participants will receive rozanolixizumab in the OLE.

Analyses will be performed by treatment group and for all study participants where stated. The treatment groups will be displayed as follows in the TFLs:

- Treatment group 1: Newly treated (ie, study participants treated with placebo in parent study)
- Treatment group 2: Previously treated (ie, study participants treated with rozanolixizumab in parent study)

Participants with the reduced dose due to tolerability issues will be mapped under the same treatment groups. These study participants will be flagged in the listings. For the Observation period the same treatment groups will be displayed.

It is expected that study participants will have received treatment as randomized in CIDP01 and hence safety and efficacy analyses will be based on the randomized treatment group in CIDP01. However, if after unblinding of CIDP01 it is determined that a study participant has received

treatment different to the treatment they were randomized to, then for safety analyses the study participant will be allocated according to the actual treatment they received.

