7 MEASUREMENTS OF TREATMENT COMPLIANCE

The study medication will be administered and monitored by the investigator or designee. Any dosing deviations (eg, incomplete infusion volume administered, infusion temporarily interrupted, infusion discontinued) will be discussed at the DEM and any actions taken regarding the analyses will be documented accordingly and discussed in the CSR.

All drug administration details (including exposure category described in [Section 10.1](#), date, start and stop time of infusion, interruptions, discontinuations, total planned volume and actual volume delivered, planned and actual infusion rates (where applicable), location of infusion site) will be listed. The reasons for any interruptions or discontinuations will be included in the listing. The duration of the infusion, in minutes, and compliance will also be calculated and presented.

Compliance, percent of planned dose administered, will be calculated based on the planned and actual volume delivered as follows:

$$\text{Percent of Planned dose administered} = (\text{Total actual volume delivered (mL})/\text{Total planned volume (mL)}) * 100.$$

Actual volume delivered and total planned volume (ie, according to Section 7.2 of protocol) will be captured in the eCRF. In case of interruption the sum of actual volumes delivered, and the total planned volume recorded into the eCRF will be used for the calculation.

There will be no specific analysis of compliance.

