- Incidence of TEAEs (overview including number and percentage of study participants with any TEAEs, serious TEAEs, discontinuations due to TEAEs, related TEAEs, TEAEs with CTCAE Grade 3 and above [or rated as 'severe' for events with no CTCAE classification], and deaths; event counts will also be included)
- Incidence of TEAEs by SOC, HLT and PT
- Incidence of TEAEs during the Dosing Period by SOC, HLT and PT
- Incidence of serious TEAEs by SOC, HLT and PT
- Incidence of non-serious TEAEs by SOC, HLT and PT
- Incidence of AEs of special interest by SOC, HLT and PT
- Incidence of AEs of interest by SOC, HLT and PT
- Incidence of TEAEs by relationship, SOC, HLT and PT
- Incidence of TEAEs by maximum relationship, SOC, HLT and PT
- Incidence of serious TEAEs by relationship, SOC, HLT and PT
- Incidence of non-serious TEAEs by relationship, SOC, HLT and PT
- Incidence of fatal TEAEs by relationship, SOC, HLT and PT
- Incidence of TEAEs by maximum intensity (mild, moderate and severe), SOC, HLT and PT

- Incidence of non-serious TEAEs above threshold of 5% of participants by SOC and PT
- Incidence of non-serious TEAEs above threshold of 5% of participants by relationship, SOC and PT
- Discontinuation due to AEs

Summary tables will contain counts of study participants, percentages of study participants in parentheses and the number of events. A study participant who has multiple events in the same SOC, HLT and PT will be counted only once in the study participant counts but all events will be included.

Adverse event summaries will be ordered by alphabetical SOC, alphabetical HLT within SOC and decreasing frequency in the treatment group.

In summaries including intensity, the CTCAE categories will be summarized according to the following categories:

- Grade 1: Mild
- Grade 2: Moderate
- Grade 3: Severe
- Grade 4: Severe
- Grade 5: Severe
- not gradable

In the case both category types are captured and the mapping to a standard intensity classification per above rule results in a class different from the standard intensity classification given in the eCRF, the worst case will be used.

These will be tabulated together with the AEs that were not classified according to CTCAE criteria i.e., all Grade 1 AEs as per CTCAE criteria will be included in the 'mild' category together with those AEs classified as mild as per the 'standard' intensity classification.

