A listing will be presented by treatment group and study participant for all AEs. This will include the onset date/time and outcome date/time of the event (including relative days), the AE duration, days since first dose of IMP, days since most recent dose of IMP, actual dose received, study period, pattern of event, severity/intensity, relationship, action taken and outcome. In addition, the listing will flag AEs that led to discontinuation, TEAEs, serious adverse events (SAEs), AEs of interest, AEs of special interest and infusion reactions.

AEs of focus (ie, TEAEs that are a review focus for rozanolixizumab or the participant population) will be summarized, in separate tables, detailing all TEAEs meeting the following criteria described below:

- Headache using the UCB-defined search criteria.
- Gastrointestinal disturbances using the UCB-defined search criteria.
- Hypersensitivity reactions using the criteria SMQ='Hypersensitivity'

- Anaphylactic reactions using the criteria SMQ='Anaphylactic reaction' and the UCB-defined search criteria.
- Injection site reactions using the UCB-defined search criteria.
- Infusion reaction collected on the eCRF AE page.
- Opportunistic infections using the UCB-defined search criteria.
- Reductions in albumin and plasma proteins using the UCB-defined search criteria.
- Effects on the kidney using the criteria SMQ='Acute renal failure'
- Drug related hepatic disorders using the criteria SMQ='Drug related hepatic disorders - comprehensive search'.

For each of the above mentioned AEs of focus the following summaries will be presented:

- Incidence of all AEoFs by SOC, HLT and PT
- Incidence of all AEoFs by Relationship, SOC, HLT and PT
- Incidence of all serious AEoFs by SOC, HLT and PT
- Incidence of all AEoFs by Maximum Intensity, SOC, HLT and PT

UCB definitions for AEoF are found in a separate document "Adverse Events (AEs) of Focus for the rozanolixizumab Program" version 1.3, dated 04 Aug 2020.

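### Dose reductions and temporary holds are listed but not counted in any planned table, although tolerability is part of the primary objective

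*Protocol*

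**What the plan says.** SAP 2.1.1 states: "The primary objective of the study is to assess long-term safety and tolerability of weekly doses of rozanolixizumab". The only safety variable in Protocol 4.1.2 that concerns a change of treatment is "TEAEs leading to permanent withdrawal of IMP", and SAP 2.2.1.2 repeats it.

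The protocol provides for lesser dose actions:

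- Reduction for intolerance such as persistent headache (6.4, 7.2, 9.1.10).
- Reduction in Part 2 for recurrent low IgG (7.2), or on restart after a low-IgG hold (6.4.1.2, 6.4.1.3).
- A mandatory hold at total IgG below 1 g/L (6.4.1.3), and an optional hold for a non-serious persisting or recurrent infection with IgG from 1 to below 2 g/L (6.4.1.2).
- An immediate stop for ALT or AST at or above 3 times ULN with symptoms, with resumption possible if a cause other than the drug is confirmed (6.4.2, Table 9-6, 9.2.1.2.1).

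On reporting, Protocol 14.3.1 says: "The action taken, time of onset relative to dosing, actual dose received, and duration of each AE will be listed only". The SAP 10.2 summary list opens with an "overview including number and percentage of study participants with any TEAEs, serious TEAEs, discontinuations due to TEAEs, related TEAEs" and closes with discontinuation due to AEs. The AE listing carries "actual dose received, study period, pattern of event, severity/intensity, relationship, action taken and outcome". SAP 3.6 says that participants on a "reduced dose due to tolerability issues will be mapped under the same treatment groups. These study participants will be flagged in the listings". For infusions, SAP 7 says: "The reasons for any interruptions or discontinuations will be included in the listing". It plans no specific analysis of compliance.

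**The concern.** Discontinuation is only the last step in a sequence of tolerability actions. Reductions and holds exist to keep a participant on treatment who might otherwise stop. A low discontinuation count can therefore mean that the full weekly dose was well tolerated, or that part of the cohort stayed only because doses were cut or withheld.

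For an extension study whose purpose includes tolerability, the number of participants who could not stay on the full weekly dose is a basic result. As planned, a reader would have to assemble it from listings of up to 76 weekly administrations per participant (24 in Part 1 plus 52 in Part 2). The one flag meant to help, in SAP 3.6, names tolerability and so does not clearly cover low-IgG reductions.

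**Working it through.** The documents give no figure to reproduce. The check has two parts: count the displays, then test whether the indirect displays could stand in for the missing count.

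**Displays.** SAP 10.2 lists 16 TEAE summaries. A dose action appears in the first (overview) and the last (discontinuation due to AEs), and both are discontinuation. It then plans 4 summaries for each of 10 AE-of-focus topics, 4 × 10 = 40 tables, with no dose action in any. A reduction or hold therefore appears in 0 of 16 + 40 = 56. SAP 10.1 defines exposure categories but specifies no exposure table. The general rule in Protocol 14.2 that categorical variables get counts does not help, because 14.3.1 is specific about action taken.

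**Indirect trace.** The disposition table (SAP 5.1) counts participants in each analysis set, so FAS minus MFAS will be visible. The MFAS (SAP 3.5.4) drops anyone whose mean dose deviates by more than 10%, or who misses more than two administrations in three months. SAP 9.1 also gives n by exposure category in the PK tables.

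SAP 10.1 defines overall exposure (%) as the mean over visits of (actual dose / reference dose − 1) × 100. Let the reduced dose be a fraction f of the full dose. This is an assumption, since doses are redacted. With k of T doses reduced and the rest given in full, exposure = (k/T)(f − 1) × 100. It falls below −10% only when k > 0.1T/(1 − f). For doses withheld and counted as zero, f = 0 and the condition is k > 0.1T.

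| Case | Smallest k, T = 24 | Smallest k, T = 76 |
|---|---|---|
| f = 0.5 | 5 (k > 4.8) | 16 (k > 15.2) |
| f = 0.7 | 9 (k > 8) | 26 (k > 25.3) |
| f = 0.8 | 13 (k > 12) | 39 (k > 38) |
| f = 0.9 | never (k > 24) | never (k > 76) |
| Held, counted as zero | 3 (k > 2.4) | 8 (k > 7.6) |

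For example, with f = 0.7 and a reduction at Week 17, 8 of 24 doses are reduced. Exposure is (8/24)(−0.3) × 100 = −10.0%, which stays in the middle category. A hold of one or two doses among 24 gives at most 2/24 = 8.3% and does not meet the missed-administration rule either.

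**Three features weaken the trace further.**

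- The reference dose is called the randomized dose in SAP 10.1 and the total planned dose in SAP 3.5.4. If the planned dose is the reduced one, a reduced participant shows no deviation at all. The same holds for the compliance percentage in SAP 7, where planned volume follows Protocol 7.2, which includes the reduced-dose table.
- SAP 10.1 does not say whether a withheld visit enters the mean as zero or drops out.
- The categories are not specific. The footnote to Protocol Table 7-1 says that full doses at 47 to 50 kg and at 63 kg can fall outside ±10% of the intended dose, so a participant can leave the middle category through weight banding alone. Doses missed for other reasons, such as COVID-19, also count.

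**The case against.** The strongest reply is that this is a single-arm descriptive extension whose primary variable is the occurrence of TEAEs, which is tabulated in depth. Planned and actual volumes, interruptions with reasons, action taken and actual dose are all listed. On that view the extra rows are a preference. The point about traceability stands, and it keeps this from being a serious defect. It does not make the count available, and choosing listings over a table was an explicit decision, so adding detail elsewhere will not fill the gap by default.

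Two further points on that side also stand:

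- A reader might infer that the planned tables say nothing about dosing, so that any number of reduced or held participants, from none to all, is compatible with them. The documents do not support that. Widespread long holds would visibly shrink the MFAS relative to the FAS and, if withheld doses count as zero, fill the PK category below −10%. The signal is partial, not absent.
- A reader might infer that the trigger for the mandatory hold goes unreported because IgG at or below 1 g/L gets only a listing flag (SAP 10.3, 13.2). That also goes too far. Protocol 6.4.1.3 speaks of an event of hypogammaglobulinemia, and 9.1.1.1 lets abnormal laboratory findings be AEs, so a recorded event is tabulated by preferred term. SAP 9.2.1 summarises each participant's minimum IgG by group, so the group minimum shows whether anyone analysed fell below 1 g/L, though not how many.

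Finally, the eCRF coding cannot be seen. Whether action taken separates reduction from interruption, and whether the interruptions in SAP 7 include a skipped weekly dose or only a paused infusion, is unknown. That limits the fix, not the finding.

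**Conclusion.** The point holds as a reporting gap that should be closed. Tolerability is in the primary objective, several protocol-allowed reductions and holds can keep a participant on study, and 0 of 56 planned AE tables counts any of them. The indirect counts are non-specific and can miss short holds and late reductions. The discontinuation count alone therefore does not show tolerance of the full weekly dose.

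The size in participants cannot be estimated: sample size and doses are redacted and no event rates are given. The thresholds for the indirect trace rest on assumed values of f from 0.5 to 0.9, on the full dose as reference, and on all other doses being given in full. A reader might infer that tolerability is untabulated or its assessment invalid. Neither follows: permanent discontinuations and the harms themselves are tabulated, individual data are listed, and no inferential result changes.

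**What to change.** In SAP 10.1, add the following by treatment group and by Part 1 and Part 2, derived from the dosing record:

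- n (%) of participants with at least one dose below the full weight-band dose for any protocol-allowed reason. Show separately those who enter CIDP04 already on a reduced dose, since Protocol 7.2 carries the parent-study dose forward.
- n (%) with at least one scheduled administration withheld under Protocol 6.4.1 or 6.4.2 and later resumed.
- Missed doses with no recorded reason, reported as missed administrations and not as holds.

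In the SAP 10.2 overview, add rows for TEAEs leading to dose reduction and to temporary interruption of IMP, where the action-taken field supports them. Extend the SAP 3.6 flag to low-IgG reductions. Record the departure from Protocol 14.3.1 in SAP 3.9.

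The cost is a few rows and short wording changes. Planned and delivered volumes are already in the eCRF (SAP 7), and the MFAS rule already needs missed administrations. No dosing rule or analysis set changes. The downsides are dependence on how the eCRF codes action taken and reasons for missed doses, and a tolerability profile that may look less favourable.
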